## List of Abbreviations

ACQ – asthma control questionnaire
COPD – Chronic obstructive pulmonary disease
EAR – Early asthmatic response
EB – Eosinophilic bronchitis
GERD – gastro-esophageal reflux disease
ICS – Inhaled corticosteroid
IL5 - Interleukin 5
LAR – Late asthmatic response
NAEB – Non-asthmatic eosinophilic bronchitis
OCS – Oral corticosteroid
RCT – randomized controlled trials
REB – Research Ethics Board
SOP – Standard operating procedure
TRPV1 – Transient receptor potential vanilloid type-1
WOCBP – Women of childbearing potential

## 1. Introduction

### 1.1. Study Summary

Cough is the most common presenting symptom to family physicians (1). Chronic Cough affects approximately 10-12% of the general population (2) and is one of the commonest reasons for referral to secondary care (3). Unfortunately, there are no licensed treatments for this debilitating condition, which is associated with a poor quality of life, affecting the social, physical and psychological well-being of patients (4). Asthma and non-asthmatic eosinophilic bronchitis (NAEB) are known causes of chronic cough and 30-50% of patients have evidence of eosinophilic airway diseases (5-7). Inhaled corticosteroids (ICS) are commonly used to treat cough in asthma and EB but there are no randomized controlled studies showing evidence of improvements in objective cough rates. Our group has recently demonstrated increased sputum eosinophils after allergen challenge to be associated with increased neuronal sensitivity and increased objectively measured cough frequency over 24 hours (8). Eosinophils have also been found to be co-localised with airway nerves (9). Increased airway eosinophilia in asthma and non-asthmatic eosinophilic bronchitis (NAEB) may be driving excessive coughing and this can potentially be targeted by anti-interleukin 5 (IL5) therapy.

Therefore, the aim of this single centre proof-of-concept study is, for the first time, to investigate whether mepolizumab reduces objective cough frequency in patients with eosinophilic asthma and NAEB presenting with chronic cough. Secondary outcomes including the effects on quality of life, intensity of irritant sensations, airway hyper-reactivity and inflammatory cells will also be evaluated.

### 1.2 Background and Rationale

#### *Chronic Cough – An Unmet Need*

Cough is the single most common reason for seeking medical attention (1). Many individuals experience acute coughing lasting up to three weeks after a viral respiratory tract infection. However, approximately 10% suffer from chronic cough (lasting more than eight weeks) with detrimental effects on quality of life (10-12). The prevalence increases with age, but peaks in the 50's and 60's and is twice as common in females than in males (13). The typical

history is described as a non-productive cough often occurring in distressing bouts, which the patient cannot control, usually preceded by an irresistible urge to cough associated with an irritating sensation in the throat. Cough can be evoked by innocuous triggers such as changes in temperature, strong smells from perfumes or aerosols, dust and passive smoking (14, 15).

Chronic cough has major psychological, social and physical consequences (16). Individuals with chronic cough are embarrassed socially and in the workplace. They become physically exhausted by the frequent prolonged coughing bouts, and women may experience stress incontinence. The treatment options for chronic cough are limited. In the US, over \$8 billion is spent each year on over-the-counter cough and cold medications, most of which contain dextromethorphan which has very limited if any clinical effectiveness (17). Unfortunately, there are no current licensed treatments for chronic cough, and this represents a major clinical unmet need.

### *Aetiology of Chronic Cough*

Chronic cough can be associated with many respiratory conditions such as asthma, NAEB, bronchitis in smokers and chronic obstructive pulmonary disease (COPD), where the cough is typically related to the pathophysiology of the underlying disease, e.g. smoking in COPD or excess airway mucus. Other causes include eosinophilic bronchitis, interstitial lung diseases, bronchiectasis or use of angiotensin-converting enzyme inhibitors. Extra-pulmonary diseases such as gastro-esophageal reflux disease (GERD) and post-nasal drip secondary to rhinosinusitis can also be identified as potential triggers.

Observational studies detailing the aetiology of chronic cough in patients presenting to specialist cough clinics show large variations in the prevalence of asthma (6-36%), GERD (0-41%), and rhinitis (8-56%) (18). Furthermore, up to a quarter of patients may have multiple aetiologies combined (19). Non-asthmatic eosinophilic bronchitis was first described in 1989 at McMaster University as a potential cause of chronic cough (20). However, as access to measuring sputum eosinophilia is limited, the prevalence of NAEB is uncertain. Studies in specialist clinics where assessments of airway inflammation in chronic cough patients have been made, report between 10-30% as having evidence of eosinophilic airways (7, 21, 22).

### *Treatments for cough in asthma and non-asthmatic eosinophilic bronchitis*

Both asthma and NAEB are associated with airway eosinophilia, but in the latter, there is no evidence of increased airway hyper-reactivity or variable airflow limitation, and cough is the predominant symptom. This has led to guidelines recommending a trial of treatment with ICS. However, the strength of the recommendation is weak due to a lack of evidence showing reduction in objective coughs rates in placebo-controlled studies (23). The use of ICS is well established in asthma from the large phase 3 randomized controlled trials (RCT), however, cough is not independently assessed in most studies, and current asthma questionnaires such as the asthma control questionnaire (ACQ) do not capture cough as a symptom. In patients with asthma or NAEB, use of inhaled corticosteroids can also make coughing worse, occasionally leading to use of low-dose oral corticosteroids. This can result in long term side effects which are intolerable to patients.

#### *Airway Nerves, Eosinophils and Cough*

Cough is the archetypal airway defensive reflex mediated by sensory afferents of the parasympathetic vagus nerves and its receptor profile on the nerve terminals. Activation of two main sub-types of sensory vagal afferent nerves is responsible for evoking cough (24):

- I. C fibres: networks of un-myelinated nerves found throughout the airways, sensitive to chemical stimuli including inflammatory mediators (e.g. bradykinin, prostaglandins) and environmental stimuli (e.g. pollutants, temperature). These nerves can be activated by capsaicin, a specific agonist of transient receptor potential vanilloid type-1 (TRPV1)
- II. A-delta fibres: proximal airways are also innervated by sub-epithelial myelinated nerves also known as 'cough receptors', as they evoke cough. They respond to punctate mechanical stimuli, low osmolarity and acidity.

To directly assess the role of airway eosinophils in asthma, coughing and neuronal sensitivity, we previously performed whole lung allergen challenge in patients with mild steroid naïve atopic asthma who demonstrated both an early and late asthmatic response (EAR/LAR) to inhaled allergen (8). We showed that capsaicin evoked coughs increased during the early asthmatic response but also remained heightened 24 hours after allergen when

bronchoconstriction had resolved. This heightened cough response was associated with an increase in sputum eosinophils from 3% to 15% and also increased objective hourly cough frequency. This suggests that in individual patients, an increase in airway eosinophilia, increases neuronal sensitivity which enhances the cough reflexes, resulting in an increase in spontaneous coughs. How eosinophils actually sensitise airway nerves is still unknown, however recent wholemount imaging studies in moderate to severe asthmatics has shown greater co-localisation of eosinophils and airway nerves in patients with moderate-severe asthma compared with healthy controls and patients with mild asthma (9). Furthermore, in an animal model, eosinophils mediated an increase in nerve density (9).

#### *Mepolizumab as a treatment for chronic cough in eosinophilic airways diseases*

Mepolizumab is a humanised monoclonal antibody against IL-5, which is currently licensed for treatment in patients with severe uncontrolled exacerbations. Interleukin-5 is a key cytokine controlling eosinophil growth, differentiation, recruitment, activation and survival (25-27). Treatment with mepolizumab results in a reduction in serum eosinophils and sputum eosinophils (28, 29). The main clinical benefits are in the reduction in exacerbations requiring treatment bursts of oral corticosteroids (OCS) and/or hospitalisations by approximately 50-60% (29, 30). There have been no studies which have recruited patients with chronic cough or assessed objective cough frequency as a study outcome with anti-IL5 therapy.

Therefore, the aim of this study is to evaluate the effectiveness of mepolizumab for the treatment of chronic cough in patients with eosinophilic airways disease, including both asthma and NAEB.

## **2. Hypothesis**

We hypothesise that in patients with asthma and NAEB, eosinophils are involved in sensitising airway nerves and thereby increasing spontaneous objective coughs. We therefore predict that treatment with mepolizumab will reduce airway eosinophilia in patients with chronic cough due to eosinophilic asthma and NAEB, thereby causing a reduction in objective cough frequency.

### **3. Study Aim**

This is a proof-of-concept study to investigate if anti-IL-5 treatment aimed at reducing airway eosinophilia causes a reduction in objective cough frequency.

### **4. Study Objectives**

#### **Primary Objectives:**

In patients with refractory chronic cough with airway eosinophilia to measure the effects of mepolizumab on 24-hour objective cough frequency.

#### **Secondary Objectives:**

1. To determine the effects of mepolizumab on:

- i. Awake /Night-time cough frequency
- ii. Intensity of irritant sensations
- iii. Quality of life
- iv. Airway hyper-responsiveness
- v. Inflammatory cells

All the above secondary objectives will also be analysed based on disease group, i.e., asthma and NAEB.

[figure not shown]
2. The relationship between change in cough frequency and change in eosinophils

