### **5. Study Design**

#### **5.1. Design**

This is a 9-visit randomized, double-blind, placebo controlled, parallel group study evaluating the effectiveness of 4 doses of mepolizumab for the treatment of refractory chronic cough in patients with eosinophilic airways disease (Figure 1). We plan to complete 15 subjects in each arm of the clinical trial. The duration of intervention will be 12 weeks, during which

subjects will receive 4 doses at days 0, 28, 56 and 84. The effects of mepolizumab on objective cough frequency will be tested at week 14, 2 weeks following the last dose of mepolizumab/placebo.

**Figure 1.** Study flow diagram detailing the study visits and procedures per visit per subject following enrolment.

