#### **D. Methacholine Challenge Test**

Methacholine is a synthetic form of acetylcholine and therefore causes smooth muscle contraction. It is commonly used in clinical practice to exclude asthma, but also as a measure of airway hyper-responsiveness. It involves giving nebulised methacholine in doubling concentrations from 0.0625 mg/mL up to 16 mg/ml via the 2-minute tidal breathing method. At each concentration, FEV1 is measured 30s and 90s after the end of each inhalation. The % fall in FEV1 from baseline is calculated after each dose using the best FEV1 and the test is terminated once a 20% fall in FEV1 (PC20) is documented or the maximum concentration of 32 mg/mL is reached. Patients with a methacholine PC20<16mg/ml will be considered to have asthma. The methacholine PC20 will be assessed at Visit 1 and Visit 9. Information about which medication to stop prior to the test will be given to the patient.

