### **5.13. Blinding and Randomization**

Subjects will be assigned to one of the two possible treatment arms generated by a computer-generated randomisation schedule prepared by McMaster University, with a ratio of 1:1, mepolizumab or placebo. As there is a known imbalance in the prevalence and cough rates, the study will include sex as a randomisation factor. This will mitigate the possibility of the intervention being confounded by sex differences in the 2 arms of the study. Blinded study drug supplies will be provided in sequentially numbered identical syringes in accordance with the randomisation schedule and dispensed by a pharmacist who shall not be delegated any other role in the study. Subjects, investigators, research staff (with the exception of the pharmacist) and the sponsor will be masked to the treatment sequence assignment. A sealed code-break envelope for each subject containing details of the treatment allocated will be kept in a locked safe at the study site.

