## **6.7. Concomitant Medications**

Patients will be allowed to have the COVID-19 vaccination before or during the whole study duration. Any adverse effects related to vaccination will be assessed for severity by the study physician.

Patients with long standing asthma on stable doses of ICS or a combination ICS/long-acting-beta agonists (LABA) will be allowed to continue using these medications so long as the dose does not change during the study. Patients with asthma who experienced an asthma exacerbation during the treatment period will be allowed oral prednisone, with or without antibiotics, as is the current standard of care. Patients with non-asthmatic eosinophilic bronchitis who have tried ICS or a leukotriene receptor antagonist (LTRA) but for whom cough has not

improved will not be allowed to continue using ICS and LTRA and will require a washout period of 28 days prior to screening. Patients with non-asthmatic eosinophilic bronchitis with partial relief on ICS will be allowed to continue using these medications so long as the dose does not change during the study. Patients on a long-acting muscarinic antagonist (LAMA) will be required to undergo a washout period for 28 days prior to screening. Patients using SABA or LABA (in an ICS combination inhaler) will be required to withhold from using the inhaler 8 and 48 hrs prior to any methacholine challenges tests as per local SOP.

Medications not allowed are as followed: opioids (including codeine, tramadol, morphine), neuromodulators (including pregabalin, gabapentin, amitriptyline), ACE inhibitors, immunosuppressive medication (including but not limited to: methotrexate, cyclosporine, azathioprine, intramuscular long-acting depot corticosteroid, oral corticosteroid, or any experimental anti-inflammatory therapy) within 3 months of date of informed consent, and other biologics within 4 months or 5 half-lives prior to date of randomization. If the subject has been on an opioid or an opioid like medication for a long period of time for a longstanding medical condition other than chronic cough, such as but not restricted to chronic pain, neuropathic pain or fibromyalgia, then they will be allowed to continue on their usual dosage.

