### **7.2. Secondary Outcomes**

In patients with refractory chronic cough with airway eosinophilia to measure changes from baseline after 8 and 14 weeks of treatment with mepolizumab compared with placebo of:

1. Awake cough frequency (coughs/hr)
2. Night-time cough frequency (coughs/hr)
3. Percentage of participants with a reduction in 24-hour cough frequency of  $\geq 30\%$

4. All cough outcomes by disease group (asthma and NAEB)
5. Cough severity and intensity of sensations (itch, tickle, irritation, urge to cough on a modified Borg Scale)
6. Quality of life measured using the Leicester Cough Questionnaire (LCQ)
7. Blood eosinophils
8. Sputum Eosinophilia (% cell count)

To determine changes from baseline after 14 weeks of treatment with mepolizumab compared with placebo of:

1. Methacholine PC20
2. Total, activated mature eosinophils, eosinophil progenitors in blood and sputum (Flow cytometry) and related transcriptomics.

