### 9. Statistical Plan

#### 9.1. Sample Size Estimation

It is assumed that 60 subjects will be screened to randomize 30 subjects, and 15 will be randomized to complete each treatment arm in 1:1 ratio. This is a proof-of-concept study investigating the effectiveness of mepolizumab on objective cough rates in patients with

eosinophilic asthma or NAEB. As such, no formal power calculation can be currently performed. The sample size is therefore based on previous similar pilot studies using cough monitoring as an endpoint (36, 37).

With 15 patients per arm, this study will have 80% power with an alpha of 5% to detect an estimated 20% greater reduction in 24hr cough frequency compared with the placebo arm, assuming a log standard deviation of 0.60. A clinically relevant reduction in cough frequency of 20% was established following a recent phase 3 studies of gefapixant in refractory chronic cough which showed a 20% reduction over placebo as significant (38). The data from this study will be used to estimate the sample size required for any future multi-centre studies.

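### The asthma and NAEB analyses include no treatment-by-disease estimate, so a chance contrast between the two diseases could be read as a real one

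*Combined protocol and SAP*

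**What the plan says.** Section 4 lists secondary objectives 1.i to 1.v (awake and night-time cough, irritant sensations, quality of life, airway responsiveness, inflammatory cells) and then says: "All the above secondary objectives will also be analysed based on disease group, i.e., asthma and NAEB". Objective 2, the relation between change in cough and change in eosinophils, comes after that sentence and is outside it. Section 7.2, item 4, repeats the commitment for changes at weeks 8 and 14: "All cough outcomes by disease group (asthma and NAEB".

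Disease group is defined in section 5.11 D: "Patients with a methacholine PC20<16mg/ml will be considered to have asthma". NAEB is the remainder by implication. PC20 is measured at Visits 1 and 9.

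On size and allocation, section 9.1 expects that "60 subjects will be screened to randomize 30 subjects", and section 5.1 says "We plan to complete 15 subjects in each arm of the clinical trial". Section 5.13 allocates "with a ratio of 1:1, mepolizumab or placebo", and "the study will include sex as a randomisation factor". Disease group is not named as a factor, and no expected asthma/NAEB split or quota is given.

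On method, section 9.2.2 specifies a GEE whose only named covariate is baseline cough frequency. Section 9.2.3 carries that approach to cough frequency, LCQ, Borg scores and eosinophils, uses a chi-squared test for the 30% responder outcome, and uses a t-test or Mann-Whitney test for inflammatory cells and PC20. Section 9.2.1 sets significance at p<0.05. None of these mentions disease group, an interaction, a multiplicity rule or an exploratory status for the disease-group results.

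Section 6.7 says that NAEB patients whose cough did not improve on ICS or an LTRA "will not be allowed to continue using ICS and LTRA and will require a washout period of 28 days prior to screening". NAEB patients with partial relief on ICS, and patients with long-standing asthma on stable ICS or ICS/LABA, may continue.

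**The concern.** If the stated approach is applied to asthma and to NAEB in turn, each outcome yields two treatment p-values and no estimate of whether the treatment effect differs between the diseases. A significant result in one group beside a non-significant result in the other is easily reported as a drug that works in one disease only. That comparison is not a test of a difference. In groups this small it arises often when the true effect is the same in both.

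Two features of the design add to the problem. Disease group is not a randomisation factor, so the arms may be uneven within a disease. Background ICS use also differs in part by disease under section 6.7, so even a real difference between the groups could not be put down to the disease alone.

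**Working it through.** **Inputs.** From section 9.1: 15 per arm, log SD 0.60, a 20% greater reduction than placebo, alpha 5%. My assumptions: natural logs, a two-sided test, and a two-sample t-test standing in for the baseline-adjusted GEE. The documents give no disease split, so I use three: 15/15 (8 v 7 and 7 v 8 by arm), 20/10 (10 v 10 and 5 v 5) and 24/6 (12 v 12 and 3 v 3).

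**1. The plan's own power figure.** The difference is −ln(0.80) = 0.223. SE = 0.60 × √(1/15 + 1/15) = 0.219. The ratio is 1.02 against a critical t(28) of 2.05. Noncentral-t power is 16.6% (17.3% by the normal approximation), not the stated 80%. At SD 0.60, 80% power needs a difference of 0.636, which is a reduction of 1 − exp(−0.636) = 47%. I therefore carry two effects: 20%, the plan's own, and 47%, the effect at which the claimed power would be true. Only the ratio of effect to SD matters, so a 20% effect with an SD of about 0.21 gives the same results as the 47% case.

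**2. Separate tests in each disease, same true effect in both.** SE in a group = 0.60 × √(1/n₁ + 1/n₂): 0.311 for 8 v 7; 0.268 and 0.379 for 20/10; 0.245 and 0.490 for 24/6. With powers p and q in the two groups, the chance that exactly one is significant is p(1−q) + q(1−p), computed from unrounded powers.

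| True reduction in both | Split | Power in each group | Exactly one significant | Both | Neither |
|---|---|---|---|---|---|
| 20% | 15/15 | 0.102, 0.102 | 18.4% | 1% | 81% |
| 20% | 20/10 | 0.124, 0.082 | 18.5% | 1% | 81% |
| 20% | 24/6 | 0.141, 0.065 | 18.7% | 1% | 80% |
| 47% | 15/15 | 0.475, 0.475 | 49.9% | 23% | 28% |
| 47% | 20/10 | 0.611, 0.315 | 54.1% | 19% | 27% |
| 47% | 24/6 | 0.699, 0.172 | 63.0% | 12% | 25% |
| none | any | 0.05, 0.05 | 9.5% | 0.3% | 90% |

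The 9.5% counts both directions. In favour of the drug it is 2 × 0.025 × 0.975 = 4.9%. At an even split 2p(1−p) cannot exceed 50%, so the 47% case is close to the worst for 15/15.

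**3. The missing estimate.** At 15/15 the treatment-by-disease contrast has SE = 0.60 × √(1/8 + 1/7 + 1/7 + 1/8) = 0.439, twice the 0.219 of the overall effect. With t(26) = 2.056, exp(2.056 × 0.439) = 2.47, so the 95% CI for the ratio of the two effects is the estimate times or divided by about 2.5. At 24/6, SE = 0.60 × √(2/12 + 2/3) = 0.548 and the factor is exp(2.056 × 0.548) = 3.1. When the effects are equal, a test of this contrast is falsely positive in 5% of trials per outcome. Its power is about 8% if the reduction is 20% in one disease and zero in the other.

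**4. Arm balance within a disease.** If 15 of 30 patients have asthma and 15 of 30 receive mepolizumab, the hypergeometric probability that a disease group splits 10:5 or worse between arms is 14%.

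**5. Several outcomes.** I take six outcomes with an assumed correlation of 0.5 to 0.9, a 15/15 split, and significance counted only in favour of the drug. In 20,000 simulated trials per setting, at least one outcome was significant in exactly one disease in 34-53% of trials at 20%, 78-96% at 47%, and 11-20% with no effect.

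**The case against.** The strongest reply is that the plan never says it will run two separate tests at 0.05 or compare their p-values. It says only that outcomes will be analysed by disease group, and these are secondary analyses in a 30-patient proof-of-concept study. That stands as a reading of the text: the firm finding is that the method is not given and that nothing stated estimates a difference between the diseases. It does not remove the problem, because following section 9.2 as written produces exactly those within-disease p-values.

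The documents also do not support several stronger readings that a reader might infer:

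- *A false contrast is likely.* On the plan's own effect and SD it occurs in about 18% of trials per outcome, and the usual result, about 80%, is that neither group is significant. It reaches half only with a much larger effect, or over several outcomes under assumed correlations.
- *There will be about 15 patients per disease.* The 15 in the protocol is the size of a treatment arm.
- *The disease result will choose the population of a later trial.* Section 9.1 says only that the data will be used to estimate a future sample size.
- *ICS use biases the treatment effect.* The rules in section 6.7 apply to both randomised arms alike. They confound only a comparison between diseases, and only in part, since NAEB patients with partial relief may stay on ICS.

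It is also fair that an interaction test would settle little at this size. That is a reason to show its interval and not to treat it as decisive.

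**Conclusion.** The concern holds in limited form. Sections 4 and 7.2 commit to asthma and NAEB analyses for which section 9.2 offers no treatment-by-disease estimate. With an identical true effect in both diseases, exactly one would be significant in about 18-19% of trials per outcome at a 20% reduction, 50-63% at a 47% reduction and 9.5% with no effect. These figures rest on splits between 15/15 and 24/6, a natural-log SD of 0.60, a two-sided 5% t-test, and the natural but not explicit reading that each disease is tested on its own. The first range barely moves with the split; the second rises as the split becomes more uneven.

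The pooled primary comparison is unaffected. The weakness lies in a stated secondary objective that could be misreported, and the remedy is cheap, so the change should be made.

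**What to change.** In sections 7.2 and 9.2.3:

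- Label the disease-group analyses exploratory.
- For continuous outcomes, fit one model to all participants with treatment, disease group, treatment-by-disease and the baseline value. Fix disease group from the Visit 1 PC20, not from Visit 9, which follows treatment.
- Report the treatment effect in each disease, and the interaction as a ratio (a difference for untransformed outcomes), all with 95% CIs.
- State that no claim will be made from separate within-group p-values.
- For the 30% responder outcome, report proportions and risk differences with CIs by disease group, because an interaction model may not be estimable with so few patients per cell.
- Tabulate background ICS use by disease beside these results, and state the expected asthma/NAEB split.

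Adding disease group to the primary model is optional; this point does not require it.

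The costs are a protocol amendment under section 9.4, best made before unblinding; one or two degrees of freedom; and more cautious wording on single-disease results. The interaction estimate will be imprecise (times or divided by about 2.5 at 15/15), so it should be presented as an estimate and not as a decisive test. No new data, visits or patients are needed.

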## 5.5. Study Population

Male and female patients  $\geq$  18 years of age assessed in a secondary care clinic for chronic cough due to asthma and/or NAEB.

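### Results are promised by disease group, but disease group is neither a named randomisation factor nor a covariate in the primary model, although it is known before allocation.

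*Combined protocol and SAP*

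**What the plan says.** Section 5.5 admits patients with "chronic cough due to asthma and/or NAEB". Sections 5.5 to 5.7 set no quota, cap or minimum for either disease.

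By-disease results are promised twice. Section 4 says of the first set of secondary objectives: "All the above secondary objectives will also be analysed based on disease group, i.e., asthma and NAEB". Section 7.2 lists all cough outcomes by disease group among the secondary outcomes, at weeks 8 and 14.

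Allocation is described in section 5.13: "As there is a known imbalance in the prevalence and cough rates, the study will include sex as a randomisation factor", "with a ratio of 1:1, mepolizumab or placebo". No other factor is named and no block size is given. The model in section 9.2.2 is a GEE with baseline cough frequency as the one stated covariate; neither sex nor disease group appears. Section 9.2.3 gives no method for the by-disease analyses.

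The classifying rule is in section 5.11 D: "Patients with a methacholine PC20<16mg/ml will be considered to have asthma". The test is done at Visit 1 and again at Visit 9. Under section 5.10.1, randomisation follows the screening visit, so disease group is available when a patient is allocated.

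**The concern.** Section 5.13 justifies sex as a factor because it is related to cough and could otherwise confound the comparison. The same reasoning applies to disease group. Section 1.2 says NAEB lacks the airway hyper-reactivity and variable airflow limitation of asthma. Section 6.7 sets different background-treatment rules for the two diseases. An arm with more NAEB may therefore also differ in inhaled steroid use, and adjusting for baseline cough need not absorb that.

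Two things are at stake. If cough change differs between the diseases, an uneven mix moves the primary treatment estimate in the trial actually run, and section 9.1 intends to use these data to size later studies. Within the smaller disease group, an uneven split widens an interval that is already wide. Because no by-disease method is stated, the analyst would have to choose one after seeing the data.

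**Working it through.** **The plan's own figures.** The plan gives no expected asthma/NAEB split and no calculation for the by-disease analyses, so there is no figure on this point to reproduce. The inputs taken from section 9.1 are 15 per arm, a log SD of 0.60 and a 20% greater reduction, i.e. |ln 0.8| = 0.223. I read the SD as a natural-log, per-patient SD; the log base is not stated. With these inputs the stated 80% power does not reproduce: SE = 0.60 × √(2/15) = 0.219, and Φ(0.223/0.219 − 1.96) = 0.17. That is a separate matter. Nothing below depends on the 80%, but the SE of 0.219 is used.

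**1. How often the mix is uneven.** Let K of the 30 patients belong to the smaller disease group. With 15 per arm, and disease taken as independent of sex, the number in one arm is hypergeometric: P(X = x) = C(15, x) C(15, K − x) / C(30, K).

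| K of 30 (assumed) | Arms differ by 4 or more | One arm has at most 1 | One arm has none |
|---|---|---|---|
| 15 | 0.143 | <0.001 | <0.001 |
| 12 | 0.264 | <0.001 | <0.001 |
| 10 | 0.245 | 0.005 | <0.001 |
| 9 | 0.109 | 0.014 | 0.001 |
| 6 | 0.169 | 0.169 | 0.017 |
| 3 | not possible | 1 | 0.224 |

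For K = 10 in full: P(X ≤ 3) = (3,003 + 75,075 + 675,675 + 2,927,925) / 30,045,015 = 0.1225. Doubling for both arms gives 0.245. The other 75% of allocations split 5:5 or 4:6.

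**2. What an uneven mix does to the primary contrast.** A 3:7 split puts the arms 4/15 = 27 percentage points apart in NAEB share. Suppose mean log cough change differs between the diseases by g. The documents give no value; I take g = 0.25 to 0.5 as an assumption.

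- Shift = (4/15) × g = 0.067 to 0.133.
- Against the SE: 0.067/0.219 = 0.3 and 0.133/0.219 = 0.6.
- Against the target effect: 0.067/0.223 = 30% and 0.133/0.223 = 60%.

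Averaged over all allocations at K = 10, the mean absolute imbalance is 13 points, so the mean absolute shift is 0.133 × g = 0.03 to 0.07. The SD of the imbalance is 0.175, so the variance of the shift is (0.175 × 0.25 / 0.219)² = 4% to (0.175 × 0.5 / 0.219)² = 16% of the sampling variance.

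**3. What it does within a disease.** With 10 NAEB patients, the variance at 3:7 relative to 5:5 is (1/3 + 1/7)/(1/5 + 1/5) = 1.19, a 9% wider standard error. With SD 0.60 and t on 8 df (2.306), the 95% interval for the ratio is the estimate multiplied and divided by exp(2.306 × 0.379) = 2.40 at 5:5, and by exp(2.306 × 0.414) = 2.60 at 3:7.

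**4. What balance would buy.** With the smaller group split as evenly as possible, its two-sided power for a 20% reduction is 10% at 8 v 7, 8% at 5 v 4 and 6.5% at 3 v 3. The interval factors are 1.96, 2.6 and 3.9.

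**The case against.** The strongest reply is that nothing here is an error in the allocation. A randomised comparison is valid without stratifying on every prognostic factor; chance imbalance adds variance, not bias, and the standard error allows for it. Section 5.13 gives a reason for choosing sex, and one factor in 30 patients is defensible. All of this stands. A reader might infer that the design biases the treatment comparison, but the documents do not support that.

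The shift on the primary rests on a disease difference that has no source in the plan. The shared eosinophil mechanism in section 2 does not point to a large one, and the upper value of 0.5 is more than twice the target effect. That also stands: 0.3 to 0.6 of a standard error is what a fairly uneven split would do under a stated assumption, not a forecast.

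A reader might also infer that a by-disease comparison could become impossible. An arm with at most one patient of a disease is realistic only if that disease has about 6 or fewer of 30, and the documents give no reason to fix the number there. Nor would stratifying rescue these analyses, since step 4 shows they stay imprecise under perfect balance.

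A second randomisation factor also has practical costs: four sex-by-disease strata in 30 patients, and syringes numbered in advance against a prepared schedule. Blocks of 4 could still leave a difference of up to 4 within a disease. This makes the randomisation change optional, but it does not touch the covariate.

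Finally, the grouping is not fully clean. Section 5.5 allows asthma and/or NAEB, and section 6.7 refers to patients with established asthma, who could have a Visit 1 PC20 of 16 mg/mL or above. That is a reason to write the rule down, not to leave disease group out.

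**Conclusion.** The point holds as a cheap improvement to the analysis, not as a fault in the randomisation. The plan promises results by disease, has the classification in hand before allocation, and uses it in neither the allocation as described nor the primary model.

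A noticeable imbalance is a realistic chance event: the arms differ by four or more patients with probability 0.11 to 0.26 when the smaller group is 6 to 15 of 30. Its effect on the primary estimate is moderate at most, 0.07 to 0.13 on the log scale for a 3:7 split of 10 NAEB patients.

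This rests on an assumed disease split, an assumed disease difference of 0.25 to 0.5, independence of disease and sex, and the plan's SD of 0.60 read as a natural-log value. The gap in specification (no covariate and no by-disease method) does not depend on any of these.

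**What to change.** In section 9.2.2, prespecify disease group (Visit 1 PC20 below 16 mg/mL versus not) as a covariate beside baseline cough frequency, and include sex because it is a randomisation factor. Keep the primary treatment estimate from that model. In section 9.2.3, state that by-disease effects come from the same model with a treatment-by-disease term added, reported as descriptive with 95% confidence intervals and no claim of significance within a disease. State also that the Visit 1 rule fixes the group for analysis, including for patients who enter with an asthma diagnosis.

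The cost is a few lines of text and one or two degrees of freedom. No new test is needed.

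Optional, if the randomisation schedule is not yet fixed: add disease group as a second factor in section 5.13, with small blocks. This reduces lopsided splits, but power within the smaller group stays at about 10% or less.

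Section 5.11 D gives the highest methacholine concentration as both 16 and 32 mg/mL. The two statements must be reconciled, because this test defines the groups.
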